Quadratus lumborum block versus transversus abdominus plane block for pain management after donor nephrectomy

NCT 03476850

April 17, 2019

Medical University of South Carolina Protocol
--

PI Name: [name] MD

Study Title: Quadratus lumborum block versus transversus abdominus plane block for pain management after donor nephrectomy

TABLE OF CONTENTS

- A. Specific Aims – Page 1**
- B. Background and Significance – Page 1**
- C. Preliminary Studies – Page 1**
- D. Research Design and Methods – Page 2**
- E. Protection of Human Subjects – Page 3 - 5**
- F. References- Page 5**

A. SPECIFIC AIMS

The purpose of this study is to test a hypothesis. We hypothesize that quadratus lumborum (QL) block provides superior pain relief to the transversus abdominis plane (TAP) block during the first 24 hours after donor nephrectomy.

B. BACKGROUND AND SIGNIFICANCE

Donor nephrectomy is an altruistic operation in which the donor graciously donates one healthy kidney to another individual with renal failure. Unfortunately, the surgery to remove the graft is often associated with significant pain for the donor.^{1,2} Over the years many techniques have been employed to reduce pain for the donor, including using laparoscopic versus open surgical techniques, multimodal analgesia, and a variety of regional anesthesia techniques.³⁻⁷ Currently at MUSC, post operative pain management for patients undergoing donor nephrectomy is provided by a combination of a quadratus lumborum or TAP block, multimodal analgesics, and narcotics. The quadratus lumborum block, is a more recently developed peripheral nerve block that promises to offer improved analgesia over TAP block.^{7,8} QL has been shown to provide superior analgesia in Caesarean sections⁹ and in pediatric patients undergoing lower abdominal surgery.¹⁰ Should the QL demonstrate superior analgesia than the TAP block, it may replace the TAP as the standard block for this surgery. Concerns in the postoperative course for laparoscopic donor nephrectomy patients include pain control and side effects from opioids, including nausea/vomiting, constipation, and pruritis. Regional techniques have been included in early recovery after surgery protocols (ERAS) protocols for laparoscopic donor nephrectomy because they provide analgesia while preventing or circumventing some of these side effects. Should the QL be shown to provide superior analgesia, in the future it may be considered a component in such fast track protocols to facilitate faster time to discharge and decrease hospital length of stay.¹¹

Quadratus lumborum has been demonstrated to provide superior analgesia to TAP block in pediatric patients undergoing lower abdominal surgery and parturients undergoing Caesarean section, however no studies have compared these blocks in the laparoscopic donor nephrectomy population.^{9,10}

C. PRELIMINARY STUDIES

Currently, at our institution, TAP or QL blocks are routinely performed for laparoscopic donor nephrectomy based on provider preference. Previous studies regarding quadratus lumborum block have been thoroughly reviewed.^{7-10, 12-13} The principal investigator has previously completed a prospective, randomized clinical trial comparing the efficacy of regional anesthesia techniques for post operative pain management after total knee replacement surgery. The design of the proposed study is comparable to the previously completed study.

D. RESEARCH DESIGN AND METHODS (including data analysis)

This will be a prospective randomized double-blinded trial to compare TAP block versus QL block for pain management in living donor nephrectomy patients. Participants will be blinded to the type of block received and physicians will be blinded both intra- and post-op regarding which block patients received. The team who performs the block will know which block the patient received. No one else involved in the care of the patient will know. The surgery team will not know, and the primary (in the OR) anesthesia team will not know. None of the providers involved in post-operative care of the patient will know.

It is expected that the QL block will provide superior pain control and for a longer duration. Specifically, both groups are expected to show an increase in pain as the block wears off but those who received a TAP block are expected to show an earlier rate of pain increase.

The primary outcome of interest will be patient reported pain on the 10 point NRS scale¹⁴ measured initially in the recovery room (PACU) and then collected at "random" times by the floor nurses up to the first 24 hours post-op. Secondary outcomes will include opiate consumption over time, occurrence of side effects, occurrence of block related issues, PACU length of stay, and hospital length of stay (defined by time to meet discharge criterion).

Patients meeting inclusion criteria will be given a copy of the consent document during their pre-op visit. Consent will be obtained in holding on the day of surgery by an IRB approved, CITI certified study team member that has been trained on the protocol. Participants will be randomized to receive a bilateral TAP block or a bilateral QL block based upon a computerized randomization provided by our statistician.

After informed written consent, as part of usual clinical care, monitors will be applied and sedation provided at the discretion of the block team. Blocks will be performed under the supervision of a regional anesthesia attending experienced in the performance of both the TAP and QL blocks. Both blocks will be performed using ropivacaine 0.375% 20ml each side for a total volume of 40cc. All patients will receive standard of care pain management.

Inclusion:

Patients undergoing laparoscopic assisted donor nephrectomy

Patients that have elected to have a nerve block

18 years of age or older

Patients of ASA status I – III

Exclusion criteria:

Chronic pain or narcotic usage during the preceding 30 days

Infection at or near the intended needle insertion site

Complex or altered abdominal wall anatomy

Weight <45kg

Members of the research team will collect the following data via review of the electronic medical record:

- Total dose narcotics administered during the intraoperative period in IV morphine equivalents
- Total dose of narcotics administered in the recovery room in IV morphine equivalents
- Total dose of narcotics administered during the first 24 hours following PACU discharge in IV morphine equivalents
- Pain scores
- Date and time of discharge in order determine length of stay

Statistical Analysis:

The primary outcome of this study is NRS pain score over the first 24 hours as described by a linear mixed model which accounts for variability in frequency and number of pain assessments.

The primary outcome of interest is patient reported pain measured on a 10 point NRS scale over the first 24 hours post-op. Comparison of patient reported pain over time between the two block groups will be evaluated using a linear mixed model approach. The model will include fixed effects for block type, post-operative time, and a block by time interaction and a random subject effect to account for repeated measures on the same subject over time.

Various correlation structures will be considered and the final structure will be selected based on the model Akaike information criterion.¹⁵ We will test the hypothesis that pain measured over time differs between the two groups, specifically testing the hypotheses that the slopes of the lines for pain response over time between the two treatment groups are the same. In a study comparing patient reported pain in living donor nephrectomy, Hutchins et al. (2016) observed a median (IQR [range]) maximum patient reported NRS pain score of 6 (5-9 [0-10]) and a median minimum NRS pain score of 3 (0-4 [0-8]) in living donors who received non-liposomal bupivacaine with a transverse abdominis plane block, which is similar to our control patient population.⁶ A sample size of 24 subjects per group (48 subjects total) provides 87% power to detect a 2 point difference in patient reported pain based on a 2-sided test and significance level $\alpha = 0.05$ assuming at least 3 measures per patients and a within subject covariance having a compound symmetric structure with a standard deviation in pain score of 3 points and within subject correlation of 0.5. We will plan to enroll 52 patients (instead of 48) to account for some patients that may be withdrawn. If the within subject correlation is smaller or we have more than 3 measures on average per subject, we will be able to detect even smaller differences. Additionally, Harrell's rule of thumb states that 10 subjects per covariate are required to avoid overfitting.¹⁶ Thus the linear mixed model will also include up to 3 additional covariates, for example gender or amount of opiate consumed, in order to account for factors known to be associated with patient reported pain. MUSC has approximately 35 living donor nephrectomy patients per year and we anticipate at least 80% (28 of 35) will agree to participate in the study, thus enrollment should be completed within 2 years.

Secondary outcomes include include opiate consumption over time, occurrence of opioid side effects, occurrence of block related issues, PACU length of stay, and hospital length of stay. Comparisons between the two block groups for cumulative opiate consumption over time will also be evaluated using a linear mixed model approach, similar to what is described for patient reported pain over time. Comparisons between treatment groups for all categorical outcomes will be conducted using a chi-square test or Fisher's exact test when appropriate. Differences between treatment groups for PACU and hospital LOS will be evaluated using a two-sample t-test or Wilcoxon rank sum test when appropriate.

E. PROTECTION OF HUMAN SUBJECTS

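### NRS pain is the sole primary outcome and opioid use is tested only apart from it; if dosing follows pain the NRS difference narrows, so a supportive joint rank test is worth pre-specifying

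*Combined protocol and SAP*

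**What the plan says.** Section A sets the aim as better pain relief with the QL block than with the TAP block over 24 hours. The rest is in Section D unless noted.

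- **Primary outcome.** "The primary outcome of this study is NRS pain score over the first 24 hours as described by a linear mixed model". The null hypothesis is that "the slopes of the lines for pain response over time between the two treatment groups are the same".
- **Other analgesia.** "All patients will receive standard of care pain management". Section B says that pain management at the centre currently "is provided by a combination of a quadratus lumborum or TAP block, multimodal analgesics, and narcotics".
- **Opioid as an outcome.** It is secondary, with its own model: "Comparisons between the two block groups for cumulative opiate consumption over time will also be evaluated using a linear mixed model approach".
- **Opioid as a covariate.** The primary pain model may take up to 3 further covariates, and the amount of opiate used is one of the two examples given.
- **Data.** Pain scores are collected, with narcotic totals in IV morphine equivalents for the intraoperative period, the PACU, and the 24 hours after PACU discharge. The pain outcome runs to 24 hours post-op, so the two windows end at different times.
- **Power.** 87% for a 2-point difference: 24 per group, two-sided 0.05, SD 3, at least 3 measures, within-subject correlation 0.5.

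No analysis takes pain and opioid together, and nothing says how similar NRS with less opioid would be read.

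**The concern.** Reported pain and opioid use are two places where a better block can show. If a patient in pain is given narcotic, the score comes down and the opioid total goes up. Part of the block difference then moves from the primary outcome to a secondary one. The plan's own reasoning allows for this. It counts opiate amount among factors associated with reported pain, and Section B values regional techniques partly because they avoid some opioid side effects.

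Two things are at stake. The primary test may have less power than planned, because the sample size allows for no narrowing of the 2-point difference. And similar pain with less opioid, a plausible result if QL works, would arrive as a negative primary result beside one of several secondary findings, with no pre-specified way to read the two together.

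**Working it through.** **1. The plan's own figure.** Under compound symmetry, the SD of a patient's mean of 3 scores is 3 × √((1 + 2 × 0.5)/3) = 2.449. The standard error of the arm difference is 2.449 × √(2/24) = 0.707. Two-sided power for 2 points is Φ(2/0.707 − 1.96) = Φ(0.868) = 80.7% (79.1% with the t distribution), not 87%. A one-sided test gives 88.2% (t: 87.3%), and a correlation of 0.34 instead of 0.5 gives 87.0%. The protocol does not settle which was used. That is a separate matter; 80.7% is the starting point here.

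**2. Level and slope.** For 3 equally spaced scores, the slope test depends on last minus first, with SD 3 × √(2 × (1 − 0.5)) = 3 and standard error 3 × √(2/24) = 0.866. Power for a 2-point divergence is Φ(2/0.866 − 1.96) = Φ(0.349) = 63.7%. The level calculation comes closer to the stated 87%, so steps 3 to 6 concern mean level, not the slope hypothesis.

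**3. Effect of narrowing, with the spread held fixed.**

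| Observed difference | Power, 24 per arm | n per arm for 80% |
|---|---|---|
| 2.0 | 80.7% | 24 |
| 1.5 | 56.4% | 42 |
| 1.0 | 29.3% | 95 |

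**4. Pain-triggered dosing (assumed).** The protocol gives no dosing rule, opioid SD or expected opioid difference, so this step is illustrative. A 2-point difference is taken to exist before opioid, with dosing triggered by pain. The joint test ranks each patient's mean NRS and opioid total across all patients, adds the ranks, and applies a Wilcoxon test.

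- Observed NRS difference: about 1.0 to 1.7.
- Three scores per patient: NRS power about 47–74%, joint 64–77%, gain about −2 to +17 points.
- Six scores per patient: gain about −6 to +14 points.

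The fixed-spread formula at 1.7 points gives Φ(1.7/0.707 − 1.96) = Φ(0.444) = 67%, so at 1.0 to 1.7 points it gives 29–67%. The simulated NRS power is higher, as expected if bounded scores and dosing also reduce the spread. Step 3 therefore overstates the loss under this mechanism.

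Two separately coded versions used 24 per arm, between- and within-patient variance 4.5 each, and integer scores from 0 to 10. Dosing was hourly above a patient-specific threshold near 4. Each dose lowered pain by 0.5–3 points, fading over 4 h, and the TAP mean without opioid was 5 or 6.5. With three scores they gave observed differences of 0.86–1.60 and 0.94–1.58, and gains of −0.1 to +25 and +2 to +23 points.

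**Against opioid use alone** the result is mixed. In one version the joint test had more power in all 16 settings. In another, with little variation in thresholds (SD 1) and doses lowering pain by 2–3 points, opioid alone had 67–75% and the joint test 66–74%. With threshold SD 2 the joint test was ahead, 64–73% against 51–57%.

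**5. Dosing not tied to pain.** Here the pain difference, opioid difference and pain-opioid correlation are set independently (24 per arm, 20,000 trials per setting; opioid inputs assumed). Joint power at correlation −0.3 / 0 / 0.3 / 0.6:

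| Pain difference | Opioid difference | NRS alone (t-test) | Joint test |
|---|---|---|---|
| 2 | 0 SD | about 79% | 57 / 44 / 35 / 30% |
| 1 | 0 SD | about 28% | 20 / 15 / 13 / 11% |
| 1 | 0.4 SD | about 28% | 58 / 45 / 37 / 32% |
| 1 | 0.8 SD | about 28% | 90 / 78 / 68 / 59% |

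In the last row opioid alone has about 75%, so at correlation 0.3 or 0.6 the joint test is behind it. The joint test's own type I error is 4.7–5.2%.

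**6. Claiming superiority from either test.** If NRS or the joint test, each at 0.05, could support the claim, the false-positive rate was 6.4% in one null simulation and 6.6–8.2% in another.

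**The case against.** The strongest reply is that separate reporting of pain and opioid use is conventional and nothing is concealed. Opioid consumption is the first secondary outcome listed, with its own model, so a reader would see similar pain with less opioid. A composite is an alternative design, not the repair of an error. This stands, and it limits the point to a supportive addition.

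A second reply is that the 2-point target is a difference in reported pain among patients who already receive usual care, so treating it as a pre-opioid effect builds in the narrowing. This stands too: the protocol does not say which is meant, so 1.0 to 1.7 illustrates a mechanism and does not predict the result.

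Several stronger readings are tempting and are not supported:

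- *Every patient receives narcotics.* Section D says only that care is standard; narcotics come from Section B's account of current practice.
- *Opioid use hides the block effect and a joint test recovers it.* Both need dosing to follow pain, and even then the gain can be nil or slightly negative.
- *The joint test costs at most a few points of power.* That holds only under pain-triggered dosing; step 5 shows much larger losses otherwise.
- *The trial would report no difference although QL is better.* That depends on how the results are written up.

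**Conclusion.** The point holds as a conditional one. The text establishes that NRS is the sole primary outcome, that usual care includes narcotics, that opioid use is tested only separately, and that the power calculation makes no allowance for narrowing. The size rests on assumed pain-triggered dosing and on reading 2 points as a pre-opioid effect. On those assumptions a joint test often adds useful power over NRS, and in many settings over opioid use alone, but not in all.

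This does not show that the primary outcome is wrong, and it does not justify letting the joint test carry the superiority claim, which would raise the false-positive rate (step 6). It supports an inexpensive pre-specified supportive analysis. The covariate example is a related inconsistency that needs no simulation: opioid amount is measured after randomisation and the block can affect it, so adjusting for it can remove or bias part of the effect being estimated.

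**What to change.** Keep NRS as the primary outcome and the only basis for a superiority claim. In Section D, Statistical Analysis, add to the secondary outcomes, before unblinding:

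> As a supportive analysis, a time-weighted mean NRS and the total postoperative opioid dose in IV morphine equivalents will be computed for each patient over one common 24-hour window. Each will be ranked across all patients regardless of arm, the two ranks added, and the arms compared with a two-sided Wilcoxon rank sum test. Both components will be reported beside it. This test aids interpretation, for example of similar NRS with less opioid, and cannot by itself turn a negative primary result into a claim of superiority.

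Define the start and end of that window, since the present pain and ward narcotic windows differ. Remove opioid amount from the example covariates of the primary model.

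**Cost.** A few sentences and one extra test, with no added patients or change in care. Aligning the windows needs dose times rather than totals, but the planned model of cumulative consumption over time needs those anyway. **Downside.** The rank sum has no clinical unit, and if opioid use does not differ between arms its power can fall from about 79% for NRS alone to 30–57%. That is why it should remain supportive.

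### The 87% power figure is not tied to the named primary test (equal slopes), and that test alone does not cover the 24-hour pain-relief aim

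*Combined protocol and SAP*

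**What the plan says.** - **Aim (section A).** The hypothesis is that the QL block "provides superior pain relief to the transversus abdominis plane (TAP) block during the first 24 hours after donor nephrectomy".
- **Expected pattern (section D).** "It is expected that the QL block will provide superior pain control and for a longer duration". Pain should rise in both arms as the block wears off, and "those who received a TAP block are expected to show an earlier rate of pain increase".
- **Assessments (section D).** One score is taken in PACU. Further scores come from floor nurses at unscheduled times up to 24 hours.
- **Model (section D, Statistical Analysis).** "The model will include fixed effects for block type, post-operative time, and a block by time interaction and a random subject effect".
- **Test (same section).** The sentence opens broadly, "We will test the hypothesis that pain measured over time differs between the two groups", and then narrows to "specifically testing the hypotheses that the slopes of the lines for pain response over time between the two treatment groups are the same".
- **Power (same section).** 24 subjects per group "provides 87% power to detect a 2 point difference in patient reported pain based on a 2-sided test and significance level" 0.05. The assumptions are at least three scores per patient, compound symmetry, SD 3 and within-subject correlation 0.5. The section adds that a smaller correlation, or more than three scores, would allow smaller differences to be detected.

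**The concern.** A slope difference is measured in points per unit of time. The power statement gives an effect in points only, with no time unit, time point or spacing of scores. It therefore cannot be read as the power of the slope test, and the reader cannot tell what the primary analysis can detect.

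The slope test also answers only part of the question in section A. It responds to the gap between arms widening or narrowing, and uses nothing of a gap already present at the first score that stays constant. The block term in the model could carry that part, but no contrast using it is named as primary. With the interaction in the model, the block coefficient by itself is the gap at the time origin, not the 24-hour average. A non-significant slope could thus be reported as no difference in pain relief when part of the benefit was there from the start. Leaving the contrast open also allows it to be chosen after the results are seen.

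**Working it through.** **Inputs, all from section D, Statistical Analysis:** n = 24 per arm, SD 3 (variance 9), correlation ρ = 0.5, compound symmetry, m = 3 scores, two-sided α = 0.05. Assessment times are not given, so every time below is an assumption. Power is from the noncentral t with 2×24 − 2 = 46 df; where two values appear they are t/normal.

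**1. The plan's own figure, read as a difference in mean pain.**
- Variance of a subject's mean = 9(1 + 2×0.5)/3 = 6.
- SE = √(2×6/24) = 0.707, and 2/0.707 = 2.83.
- Two-sided power = 79.1/80.7%. The stated 87% is not reproduced.
- The difference detectable with 87% power is 2.23/2.18 points, about 2.2.
- A one-sided 0.05 test gives 87.3/88.2%. This is a possible source of the figure but not an established one: ρ = 0.3 (t) or nine scores (normal) also gives 87%.

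**2. The named test, with 2 points read as the change in the gap from first to last score.**
- SE of that change over window W = W√(2×9(1 − ρ)/(24S)), where S = Σ(t − t̄)².
- At 0/12/24 h: S = 288, SE = 24√(9/(24×288)) = 0.866, and 2/0.866 = 2.31. Power is 62/64%.
- At 0/4/24 h: 68/70%. Best case, two of the three scores at one end of the window: 74/76%.
- If 2 points meant 2 per interval (a change of 4 over the window), power is over 99%. The answer depends on a unit that the plan does not give.

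**3. Same average benefit of 2 points, different time course (0/12/24 h).**

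| Gap, first to last score | Change | Slope power | Mean-difference power |
|---|---|---|---|
| 2 to 2 (limiting case) | 0 | 5% | 79% |
| 1.5 to 2.5 | 1 | 20% | 79% |
| 1 to 3 | 2 | 62% | 79% |
| 0 to 4 | 4 | over 99% | 79% |

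For a gap growing from 0 to 2 (average 1), the order reverses: slope 62%, mean 28%. Section D does not predict the exactly constant gap.

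**4. The remark about correlation.** The variance of a mean contains 1 + 2ρ; that of a slope contains 1 − ρ. At ρ = 0.3/0.5/0.7 with three equally spaced scores, power for a 2-point mean difference is 87/79/71%, and for a gap growing from 0 to 2 it is 48/62/83%. The remark is true for a mean contrast and false for a slope, which suggests that the power paragraph has a mean difference in view.

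**5. Sensitivity to timing.** With linear time, the 0–24 h mean difference is the fitted gap at 12 h, with SE² = (2/24)[6 + 4.5(12 − t̄)²/S]. Power for 2 points is 79% at 0/12/24 h, 75% at 0/8/16 h and 66% at 0/6/12 h. It is 42% at 0/4/8 h, where the 12-hour value is an extrapolation. With PACU at 0 h plus two uniformly random times per patient over 24 h (average of 400 draws), power is 76% for the mean and 40% for a slope of 2 points per 24 h. If both random times fall in the first 12 h, power for the mean is 47%.

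**The case against.** **Section D supports a slope test.** It predicts an earlier rise in pain on TAP, and a block-by-time comparison follows from that. The general hypothesis is also broader than slopes, and the model has a block term. All of this stands, which is why the slope test is called incomplete and not wrong. None of it supplies a slope unit, or a named contrast for average pain.

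**Three scores is the minimum.** With more equally spaced scores, slope power for a gap growing by 2 points is 76% at six, 87% at nine and 94% at twelve; for a 2-point mean difference it is 84%, 86% and 87%. With PACU plus random times, six scores give 67% (slope of 2 points per 24 h) and 84% (mean). So the actual power may well exceed the three-score figures. But the plan presents 87% as what three scores deliver, since it adds that more would detect smaller differences.

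**The gap need not be linear.** Pain rising in both arms, earlier on TAP, could make the gap open and then narrow. With assumed gaps of 0, 4 and 2 points at 0/12/24 h, slope power is 62% and mean power 79%. The slope test is therefore the stronger one for a gap growing steadily from zero, not for every pattern that starts equal. This is fair, and is a further reason to state the expected time course.

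**A joint test is possible.** A two-df test of block and block by time has about 72% power for a constant 2-point gap, 79% for 1.5 to 2.5, and 68% for 0 to 2 (chi-square approximation, three equally spaced scores). It is a workable third choice, but it needs its own power statement and a directional estimate.

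**Conclusion.** The concern holds. The power of the named primary test is not defined in the plan, and 87% is not obtained at the stated two-sided inputs with three scores for a 2-point mean difference (79–81%) or for a 2-point first-to-last change in the gap (62–64% equally spaced, at most 74–76%). As the only primary test, equality of slopes leaves out any constant part of the benefit claimed in section A.

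These figures rest on the plan's SD, correlation and compound symmetry, and on assessment times that had to be assumed. They do not show that the trial lacks power: more scores, or a gap growing from 0 to 4, would give the slope test ample power. What must be fixed is the naming of one primary contrast with a power statement that matches it. The 87% arithmetic and the correlation remark are lesser corrections that follow from it.

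**What to change.** Before the data are unblinded, choose one of the following.

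- **(a) Mean pain.** Make the block difference in mean NRS over 0–24 h, from the same mixed model, the primary contrast, with block by time secondary. Replace 87% with about 79–81% for 2 points at three scores, or keep 87% and state about 2.2 points. Say that this assumes scores centred near 12 h and is lower if they cluster early. This is closer to the aim in section A.
- **(b) Slope.** Keep the slope test. State the slope difference with its unit and the assumed assessment times, replace 87% with the power for that test, and delete the claim that a smaller correlation helps. Add that a non-significant slope will not be read as no difference in pain relief. This is closer to the duration expectation in section D.

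**Cost.** Either is a change of wording and needs no added enrolment, provided the recalculated power is accepted. Under (b), holding 87% for a 2-point change in the gap at three equally spaced scores would take 2×(1.960 + 1.126)²×3²/2² ≈ 43 per arm (the SD of a subject's fitted change is 3 here; normal approximation).

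The downside of (a) is lower power if the gap grows steadily from zero (28% against 62% for 0 to 2). The downside of (b) is lower power if most of the benefit is present from the start (20% against 79% for 1.5 to 2.5).

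### The stated 87% power does not follow from the plan's own inputs: a two-sided test gives 79–81%, and 87% is what a one-sided 0.05 test would give

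*Combined protocol and SAP*

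**What the plan says.** The power statement is in section D, Research Design and Methods, under Statistical Analysis: "A sample size of 24 subjects per group (48 subjects total) provides 87% power to detect a 2 point difference in patient reported pain". The same sentence gives the basis. The calculation is "based on a 2-sided test and significance level" of 0.05, "assuming at least 3 measures per patients and a within subject covariance having a compound symmetric structure", with an SD of 3 points and a within-subject correlation of 0.5.

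Three nearby statements bear on how to read it:

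- Enrolment is set at 52 rather than 48 to cover withdrawals, so the 87% belongs to 24 per group.
- A lower correlation, or more than three measures on average, is described as making smaller differences detectable. Three measures and a correlation of 0.5 are therefore the base case behind the 87%.
- The primary hypothesis is described as equality of the two groups' slopes over time.

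The plan names no formula or software for the calculation.

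**The concern.** The sentence supplies every number that a standard repeated-measures power calculation needs, so the result can be checked directly. A comparison of time-averaged means with these inputs gives about 80%, and the gap to 87% is too wide for rounding or for a choice between normal and t methods.

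This sentence is the only quantitative justification of the sample size for the primary outcome. Anyone approving the design, or later weighing a non-significant result, would take the chance of missing a 2-point difference to be 13%. On the plan's inputs it is about one in five. If a one-sided critical value lies behind the figure, the sample-size calculation also disagrees with the two-sided test that the plan declares.

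**Working it through.** **Inputs** (all from the sample-size paragraph): n = 24 per group; difference 2 points; SD 3; m = 3 measures; correlation ρ = 0.5, compound symmetry; α = 0.05, two-sided. One reading has to be supplied: the 2 points are taken as a difference in mean score averaged over the three measures.

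**Calculation on the stated basis**

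1. Variance of a subject's mean = SD² × [1 + (m − 1)ρ]/m = 9 × (1 + 2 × 0.5)/3 = 6, so its SD is 2.449.
2. Standard error of the group difference = √(2 × 6/24) = 0.707.
3. Difference divided by standard error = 2/0.707 = 2.828.
4. Two-sided power, normal approximation = Φ(2.828 − 1.960) = Φ(0.868) = 80.7%.
5. Two-sided power, noncentral t with 2 × 24 − 2 = 46 df = 79.1%.

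The plan's 87% is not reproduced. The shortfall is 87 − 80.7 = 6.3 to 87 − 79.1 = 7.9 percentage points.

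**What does return 87%**

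With the same inputs and a one-sided 0.05 test, power is Φ(2.828 − 1.645) = 88.2% (normal) or 87.3% (t, 46 df). The t figure rounds to the printed value.

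Keeping the two-sided test, 87% needs one of the following changes:

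| Change | Value needed for about 87% |
|---|---|
| Smaller SD | about 2.7 to 2.75 instead of 3 |
| Lower correlation, 3 measures | about 0.30 to 0.34 instead of 0.5 |
| More measures, correlation 0.5 | about 9 (normal) or 12 and upward (t) instead of 3 |
| More patients | 29 (normal) or 30 (t) per group instead of 24 |
| Larger difference | about 2.2 points instead of 2 |

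For the patient numbers: n = 2 × 6 × (1.960 + 1.126)²/2² = 28.6, rounded up to 29. By t, 29 per group gives 86.3% and 30 gives 87.5%. For the difference: (1.960 + 1.126) × 0.707 = 2.18. At 2.2 points, power is 87.5% (normal) or 86.1% (t).

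**Other readings, two-sided 0.05, 24 per group unless noted**

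| Reading | Power |
|---|---|
| 26 per group (all 52 evaluable), 3 measures | 82.3–83.7% |
| AR(1) correlation instead of compound symmetry | 82.4–84.0% |
| Single time point | 61.8–63.7% |
| Change score, first measure as baseline | 74.2–76.0% |
| ANCOVA, first measure as baseline | 89.2–90.4% |
| Slope test, difference growing from 0 to 2 points over 3 equally spaced times | about 62–64% |
| Slope test, slopes differing by 2 points per interval | 99.6% |

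None of these gives 87%. The AR(1) row departs from the stated covariance structure, and the plan does not describe the change-score or ANCOVA analyses.

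**The case against.** The arithmetic itself is hard to dispute. The best case on the other side concerns what it means, and it has four parts.

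- **Three measures is a floor.** The wording is "assuming at least 3 measures per patients", and scores are collected from the recovery room to 24 hours. Six measures would give 84.1–85.6% at 24 per group, or 87.0–88.2% if all 52 patients were evaluable. This shows that the trial may achieve more than 80%, but it does not rescue the statement. The plan attaches 87% to 24 per group and counts extra measures as a gain beyond it. The number of measures to expect is not documented.
- **The one-sided explanation is conjecture.** This stands. The numerical match is exact to rounding, but an unstated SD, correlation or number of measures could also have produced 87%. The finding rests on the stated inputs not giving the stated output, whatever the cause.
- **The contrast is not spelled out.** The 79–81% assumes a time-averaged mean difference, whereas the named primary hypothesis concerns slopes. This also stands as a condition on the figure. A constant 2-point difference gives a slope test no power beyond α. That mismatch is a separate issue, and the slope readings do not produce 87% either.
- **About 80% is conventionally adequate.** This is fair. The design is not shown to be unviable, and a null result would be judged mainly on its estimate and confidence interval. A stated design property that contradicts its own inputs still has to be corrected.

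**Conclusion.** The power statement is wrong as written. On the stated inputs, two-sided power for a 2-point difference in time-averaged pain is 79.1% (t) to 80.7% (normal), not 87%. The type II error is 19–21% instead of 13%. With three measures and every enrolled patient evaluable, power reaches 82.3–83.7%.

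The result assumes equal groups of 24, exactly three measures per patient, compound symmetry, and a comparison of mean scores. The practical effect is moderate, since the trial keeps roughly 80% power on this reading, but the figure that justifies the sample size must be corrected. That a one-sided test was used in the calculation is a plausible explanation, not an established one.

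**What to change.** Keep 48 evaluable and 52 enrolled, keep the two-sided 0.05 test, and restate the sentence. Suggested wording: 24 per group provides about 79% power (two-sided α 0.05; 80.7% by the normal approximation) to detect a 2-point difference in mean NRS score averaged over three measures, with SD 3 and within-subject correlation 0.5. An equivalent statement is about 87% power for a difference of about 2.2 points. State the formula or software used. If other inputs lie behind the 87%, state and justify those instead.

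The wording should name the mean difference as the contrast being powered, so that the figure is not read as power for the slope test.

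The cost is one sentence and a less favourable power figure, with no extra patients. Keeping 87% for 2 points would instead need 29–30 evaluable per group, that is 58–60 rather than 48.
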